10.2.2. Secondary Endpoints

Consistent with the secondary study objectives, the following secondary endpoints will be assessed:

- **Immunologic response. (CD4+ T cell count).** CD4⁺ T cell counts at Weeks 0 and 2, Months 1, 3, 6 and every 6 months thereafter. Time from seroconversion to immunologic failure will be compared between active microbicide and placebo/control groups. Immunologic failure is defined as two consecutive measurements of CD4+ T-cell count within or below the range of 200-250 cells/mm³, or the development of an AIDS defining illness.
- **Virologic and immunologic responses (CD4+ T-cell count) after initiation of ART.** CD4+ T-cell count and blood plasma HIV-1 RNA levels over time after initiation of ART. Time from initiation of ART to immunologic and virologic failure.
- **HIV-1 related and AIDS-defining events.** Occurrence and frequency of HIV-1 related and AIDS-defining events. Time from enrollment to time of first AIDS-defining event or death.
- **Sexual behavior, partnership status, and occurrence of social harms.** Sexual behavior over time following seroconversion at Months 0, 3, 12, and 24 months. Participants who enroll ≥3 months after seroconversion will be followed at 12 months and 24 months only.
- **HIV-1 genotypic mutations and drug resistant virus.** Prevalence of HIV-1 genotypic mutations over time and drug resistant HIV-1 virus in plasma and genital tract. Proportions of infected participants acquiring a drug resistant HIV-1 virus.

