3.2. Secondary Objectives

- To characterize the trajectory of CD4+ T-cell counts after HIV-1 seroconversion among antiretroviral treatment naïve participants assigned to an active microbicide or chemoprophylactic agent compared to control participants.
- To compare the plasma HIV-1 RNA level six months after HIV-1 seroconversion among antiretroviral treatment naïve participants assigned to an active microbicide or chemoprophylactic agent compared to control participants.

- To evaluate the prevalence of HIV-1 drug resistance mutations in plasma and genital tract specimens after HIV-1 seroconversion among participants assigned to an active microbicidal or chemoprophylactic agent compared to control participants.
- To evaluate the virologic response to initiation of antiretroviral therapy among participants assigned to an active microbicidal or chemoprophylactic agent compared to control participants in microbicide trials and by study specific analysis (for larger trials including current and future trials).
 - The proportion with HIV-1 RNA less than 50 copies/mL six months, twelve months, and twenty-four months following initiation of antiretroviral therapy
- To describe the CD4+ T-cell response to initiation of antiretroviral therapy in participants after seroconversion in microbicide trials.
 - The CD4+ T-cell increase six months, twelve months, and twenty-four months following initiation of antiretroviral therapy
- To compare the HIV-1 drug resistance profile, among antiretroviral therapy recipients, at the time of virologic failure (HIV-1 RNA >200 copies/mL at or after six months of antiretroviral therapy) in participants assigned to an active microbicidal or chemoprophylactic agent compared to control in microbicide trials and by study specific analysis (for larger trials including current and future trials).
- To evaluate the prevalence and persistence of HIV drug resistance mutations in plasma and cervical lavage fluid using more sensitive methods (which may include modified ultrasensitive assays of plasma HIV RNA) in study specific subgroups of seroconverters.
- To describe HIV-1 related (WHO Stage II) and AIDS-defining (WHO Stage III and IV) clinical events and deaths (from any cause) occurring among seroconverters with and without antiretroviral therapy.
- To compare the rate of HIV disease progression among participants assigned to an active microbicidal or chemoprophylactic agent compared to control.

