7.2. Follow-up Visits

This study utilizes two follow-up visit schedules, one based on the date of identification of seroconversion in the parent study and one based on initiation of ART use.

- Participants who have not initiated use of ART at the time of enrollment in MTN-015 will follow the schedule based on the date of identification of seroconversion, which is described in Section 7.2.1. On this schedule, follow-up visits occur at Months 1, 3, and 6 after the date of identification of seroconversion, and every 6 months thereafter. Participants may enroll anytime after seroconversion. Following the enrollment visit, the subsequent visits will be scheduled according to the seroconversion date (for example, a participant who enrolls 4 months after seroconversion would have a second visit at 6 months after seroconversion (2 months after enrollment) and then every 6 months).
- Participants who have initiated use of ART at the time of enrollment in MTN-015 will follow the schedule based on the date of ART initiation, which is described in Section 7.2.2. On this schedule, follow-up visits occur at Week 2 and Months 1, 3, and 6 after the date of ART initiation, and every 6 months thereafter.
- Participants who initiate use of ART during follow-up in MTN-015 will follow the schedule in section 7.2.1, and then switch to the schedule in Section 7.2.2 after initiation of ART use.

As it will not always be possible to conduct follow-up visits on the target dates specified above, visits may be completed at any time during allowable visit windows. For both the non-ART and ART visit schedules, the allowable visit windows are contiguous and extend from the midpoint of one visit interval to the midpoint of the next visit interval. For example, the Month 24 visit window extends from Month 21 through Month 27. For participants who do not complete scheduled visits within the allowable window, the visit will be considered missed and relevant case report forms will be completed to document the missed visit. Missed visits will not be considered protocol violations.

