9. CLINICAL MANAGEMENT

9.1. HIV-1 Infection

Study participants will be referred for HIV-1 care and treatment according to local guidelines at the time of HIV-1 diagnosis in the parent microbicide trial. Written site-specific operating procedures for referral for HIV-1 care and treatment are in place at each study site. Study site investigators have identified facilities offering psychological and social services and medical care, including antiretroviral therapy, to people infected with HIV-1 in the study countries. Some of the research sites are part of health care institutions that provide HIV-1 care and support, and can refer women to those services. Other sites have established referral agreements with programs to expand access to antiretroviral therapy, such as those funded by the US President's Emergency Plan for AIDS Relief (PEPFAR). The level of care provided at the referral sites will be at a level that meets or exceeds the community standard for HIV-1 care. At every study visit, study staff will actively follow-up on prior referrals to HIV-1 care and support services, to determine whether the participant sought the care to which she was referred, determine the outcome of the referral, and determine whether additional referrals are needed. Additional counseling also may be needed to help ensure the participant receives appropriate care. All follow-up actions, outcomes, counseling, and plans for next steps should be documented in detailed chart

notes. Results of laboratory testing in MTN-015 may be helpful in clinical management; these results will be provided to the participant and her medical provider in real-time.

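### One definition of immunologic failure serves both the seroconversion and the ART clock: it can label responding low-count ART starters as failures, and it leaves the role of ART start undefined

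*Protocol*

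**What the plan says.** Section 10.2.2 of the protocol defines the event once, under the CD4 bullet: "Immunologic failure is defined as two consecutive measurements of CD4+ T-cell count within or below the range of 200-250" (the unit is cells per cubic millimetre). A diagnosis of an AIDS-defining condition is the alternative route to the event. Any count inside or below that range qualifies, so the CD4 part works as two consecutive counts at or below 250.

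The term appears on two clocks in the same section. The first is "Time from seroconversion to immunologic failure will be compared between active microbicide and placebo/control groups". The second, in the next bullet, is "Time from initiation of ART to immunologic and virologic failure", with no separate on-ART definition of immunologic failure.

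Virologic failure is defined in Section 3.2 with a minimum time on treatment: "HIV-1 RNA >200 copies/mL at or after six months of antiretroviral therapy".

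CD4 is measured at every scheduled visit. On ART, "follow-up visits occur at Week 2 and Months 1, 3, and 6 after the date of ART initiation", then every six months (Section 7.2). Off ART, visits are at Months 1, 3 and 6 after identification of seroconversion, then every six months. Section 9.1 says of laboratory results that "these results will be provided to the participant and her medical provider in real-time", and Section 13.3 expects that CD4 monitoring may bring some women earlier treatment. Section 10.6.2 plans Kaplan-Meier curves and a stratified log-rank test for time-to-event endpoints and says nothing about ART start.

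**The concern.** An absolute CD4 threshold means different things on the two clocks. Before ART, falling to the threshold and staying there is progression. After ART starts, a low count in the first weeks mostly reflects where the woman began. With counts at Week 2 and Month 1 and no minimum time on ART, the endpoint can be met within a month by a woman whose CD4 is rising. Time to immunologic failure on ART would then largely describe CD4 at ART start. The protocol avoids the parallel problem for virologic failure with its six-month condition.

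On the seroconversion clock, a first low count can prompt ART before the confirming count, which after Month 6 is due six months later. ART start is not part of the composite, and no rule says whether on-ART counts may confirm, whether follow-up is censored, or whether ART start is a competing event. Two analysts following the text could classify the same woman differently. Death is not in this composite either. Response to ART and the between-group comparison of disease progression are both stated secondary objectives.

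**Working it through.** The protocol states no event count, power or expected failure rate for this endpoint, so there is no figure to reproduce. The check applies the definition, read as two consecutive observed counts at or below 250, to the protocol's visit schedule.

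**ART clock, without measurement error.** Assume a rise of r cells by Month 1, half of it by Week 2. Counts are start + r/2 and start + r. Both are at or below 250 whenever start ≤ 250 − r. For assumed r of 25, 50 and 75, the limits are 225, 200 and 175. Example: start 150, r = 50 gives 150 + 25 = 175 at Week 2 and 150 + 50 = 200 at Month 1. She is rising, and she meets the definition at Month 1.

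**ART clock, with measurement error.** These inputs are assumptions, not in the documents:
- a fixed count at ART start;
- mean rise by Months 1, 3 and 6 of 25/50/75 (slow), 50/75/100 (middle) or 75/100/150 (fast), with half the Month 1 rise at Week 2 and 1.4 times the Month 6 rise at Month 12;
- each woman's rise multiplied by a normal factor with mean 1 and SD 0.5, not below zero;
- measurement CV 20%.

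Share meeting the definition, fast to slow rise:

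| CD4 at ART start | Week 2 and Month 1 both low | Any consecutive pair to Month 12 | Month 6 and Month 12 both low |
|---|---|---|---|
| 100 | 91-100% | 92-100% | 29-73% |
| 150 | 66-95% | 70-98% | 15-42% |
| 200 | 28-60% | 34-73% | 6-15% |
| 250 | 6-16% | 9-25% | 1.5-3% |
| 300 | 1-2% | 1-3% | below 1% |
| 350 | about 0% | about 0% | about 0% |

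For the middle rise, counting only from Month 6 lowers the one-year share from about 88% to 28% at start 150, from 52% to 10% at 200, and from 15% to 2% at 250. The remainder at low starts is why a comparison with the pre-ART count is also needed. A woman at 150 who gains 100 by Month 6 reads 150 + 100 = 250, still inside the range after a large gain.

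**A second set of assumptions.** Take start counts as normal with SD 50, capped at 250, a Month 1 gain of 25 to 80 with half by Week 2, and measurement SD 30. At start means of 150 to 220, 17-87% meet the definition at Month 1 (59% at mean 180, gain 50). Without the cap and with higher means, the share is 7-26% at 250, 1-6% at 300 and below 1% at 350. Both models agree: the problem is large for low starts and vanishes above about 300.

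**Seroconversion clock.** Consider a woman with a first low count who starts ART before the next off-ART visit. If only ART-naive counts may confirm, she cannot become a CD4 event. If her first on-ART count may confirm, the outcome depends on how low that count still is. In the second model, 45-94% of starters at means 150 to 220 are still at or below 250 at Week 2. A separate illustration assumes untreated counts with mean 500 falling 60 cells a year and CV 20%. There, of treated women who would have been confirmed if left untreated, about 62% are missed when the Week 2 count may confirm, and all are missed when it may not. The answer turns on a rule that the text does not state and on a share treated that it does not give.

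**The case against.** Four points have weight.

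- The definition sits in the first bullet, beside the seroconversion clock, and the ART bullet does not expressly import it; an on-ART definition could be left to a statistical analysis plan. That is fair as to layout. But no other definition exists in the protocol, so the ART endpoint either inherits this one or has none, and the stated one does not suit it.
- The size depends on low counts at ART start. Treatment follows local guidelines (Section 9.1) and Section 4.1 counts most regimens as ART initiation, so starters need not all be low. This stands: the defect concerns low-count starters, not ART starters in general.
- CD4 response is already described as an increase at six, twelve and twenty-four months of ART (Section 3.2), and death belongs to a neighbouring endpoint in Section 10.2.2. True, but neither repairs the failure-time endpoint.
- Some treated progressors are still caught, through the AIDS-defining illness limb or a low Week 2 count. Section 10.2.2 even lists Week 2 among the CD4 time points in the seroconversion bullet, although that visit exists only on the ART schedule, so on-ART counts are not barred.

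The last point defeats a stronger reading that a tempted reader might adopt: that whatever share of women is treated after a first low count is the share of events lost. That only restates an assumption. A reader might also infer bias between the arms. The documents do not show it: gel assignment is blinded (Section 10.4; the condom-only arm is not), referral follows local guidelines, and loss at the same rate in both groups costs events without by itself favouring either. Section 10.3 expects ART in under 10% in the first 6-12 months, which limits the early effect, though follow-up runs to May 2013.

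**Conclusion.** The point holds, in two parts of different strength.

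On the ART clock the defect follows from the text: one absolute threshold, no minimum time on ART, no reference to the pre-ART count, and counts at Week 2 and Month 1. Its size rests on assumed start counts and rises. It is large for starts at or below about 200 (34% or more labelled failures within a year under every rise tried) and negligible above about 300.

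On the seroconversion clock the gap is one of definition. ART start has no role, so the classification of women treated after one low count is open. The number affected cannot be derived from the protocol, and no between-group bias is shown.

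The severity is moderate. These are secondary endpoints; the primary viral load comparison and its power are untouched. The 200-250 range in place of a single cut-off is a matter of wording.

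**What to change.** Give the two clocks separate definitions in Section 10.2.2, for analysis only and with no bearing on when anyone is treated.

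- **From ART initiation:** count immunologic failure only from CD4 measured at or after six months of ART, matching the virologic failure rule in Section 3.2, and judge it against the pre-ART count.
- **From seroconversion:** use ART-naive CD4 counts. The event is the earliest of confirmed low CD4, one low CD4 followed by ART start before the confirming count, an AIDS-defining illness, or death. Add a sensitivity analysis with the definition as the protocol now states it, saying whether on-ART counts may confirm.
- **Wording:** express the range as a single analysis cut-off, and reconcile the Week 2 time point in the seroconversion bullet with the visit schedules in Section 7.2.

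The cost is endpoint wording and one extra analysis. CD4 counts and ART records are already collected and deaths fall under an existing endpoint, so no visit or test is added. The change should be made before unblinded data are examined.

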5. STUDY POPULATION

The study population will consist of female participants who are identified as infected with HIV-1 during participation in microbicide clinical trials who meet the eligibility criteria listed below. Potential participants will be recruited for MTN-015

as soon as possible after identification of HIV-1 seroconversion; however, there is no time limit for MTN-015 enrollment after identification of seroconversion. With assistance from the SDMC, the Site PI or designee will identify participants who seroconvert during participation in parent microbicide trials.

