5.1. Selection of the Study Population

Composition

Female microbicide clinical trial participants who meet MTN-015 eligibility criteria will be offered enrollment in MTN-015.

Recruitment

Study site staff will recruit potentially eligible study participants. For microbicide trial participants who seroconvert prior to activation of MTN-015, study staff will retrospectively contact the participants for possible enrollment in MTN-015, unless the participants have refused further contact with study staff. For microbicide trial participants who seroconvert after activation of MTN-015, study staff will prospectively contact the participants for possible enrollment in MTN-015 at the time of identified seroconversion. All recruitment materials will be Institutional Review Board/Ethics Committee (IRB/EC)-approved prior to use.

Retention

Each site will establish participant retention procedures to target an average retention rate of 95% per year.

Site staff members may contact participants between scheduled visits in order to facilitate high levels of retention. Each site's approach to this will be specified in its retention SOP. Sites may optionally do this through various methods (e.g., home visit, phone, letter, etc).

Co-Enrollment Guidelines

Co-enrollment in other trials is permitted by this protocol. Participants will be encouraged to report to MTN-015 staff any co-enrollment in other research trials.

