10.3. Sample Size

Preliminary data from the University of Washington/Fred Hutchinson Cancer Research Center (UW/FHCRC) Primary Infection Clinic was used to estimate within and between person components of variance in individuals with early HIV-1 infection. These data are taken from 150 days to 2 years post infection and, therefore, should give reasonable estimates of the variability in viral load around the viral set point. The between person variance component is 0.52 (\log_{10} copies²/ml²) and the within person variance component is 0.096 (\log_{10} copies²/ml²).^{xv}

In the HPTN 035 trial we expect 192 seroconverters: 128 in the placebo gel and control groups and 64 in the PRO2000 and BufferGel groups assuming an effectiveness of 50% for both active microbicides. This breakdown between groups is conservative since the true effectiveness will most likely be lower. Effectiveness that is lower than 50% will slightly improve the power of this study since the numbers between the active microbicide and placebo/control groups would be more balanced.

However not all of these 192 will be available for the evaluation of the primary endpoint at one year after seroconversion since:

By the time this study is in the field, several participants will have seroconverted more than one year ago. We estimate this number to be around 20 such that we will have 172 eligible seroconverters for the evaluation of the primary objective.

Newly-infected women may have elected to terminate from the parent study and/or do not wish to enroll in this study and/or have been lost to follow-up in the parent study. Of the 172 eligible women, we estimate that 15% of the women eligible for this study will not enroll due to one of the above reasons.

We will target no more than 5% lost to follow-up per year.

Therefore we anticipate that 138 seroconverters (92 from the placebo and control groups and 46 from the active microbicide groups, assuming that the active microbicides reduce HIV acquisition by 50%) will be available for the evaluation of the primary objective one year after seroconversion. The following table gives the power to detect various differences in the viral set point between the active microbicide and placebo/control groups.

Table 7: Power Calculation for Primary Endpoint

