10.5. Participant Accrual and Retention

All seroconverters, regardless of their seroconversion date, from the ongoing HPTN 035 and 059 trials will be recruited into this study. Although some of these participants would have seroconverted more than a year ago, which would make them ineligible for the primary objective of this study, those participants could be used in the assessment of some of the secondary objectives. All newly identified seroconverters during follow-up in HPTN 035 and 059 will be recruited for this study.

Once a participant has enrolled in the study, the study site will make every reasonable effort to retain her for the entire study period. A maximum of 5% annual loss-to-follow-up of enrolled participants is targeted.

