Many other secondary analyses will be performed using the secondary endpoints described in Section 10.2.2. Time-to-event secondary endpoints will be analyzed according to the Kaplan-Meier method where differences between groups will be tested using the stratified log-rank test while secondary endpoints involving repeated assessment over time (e.g. sexual behavior) will be compared at selected time points. At each of the selected time points, comparison of the two groups will be made using Fisher exact test or Wilcoxon rank-sum test as appropriate. More generally, GEE (Generalized Estimating Equation) methods and robust variance estimates will be used to evaluate group.

Data on behaviors that are associated with HIV-1 transmission such as sexual intercourse without a condom, the frequency of sexual intercourse, and the numbers of sexual partners will be measured over time among women in this study and compared to the same behaviors reported by women in ongoing microbicide trials (including parent trials) who are HIV-1 negative and to large household surveys of women (Demographic Health Surveys) in the same countries as the women in this study are located.

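### AIDS-defining event or death is timed from MTN-015 enrollment, a date unrelated to duration of infection, while the neighbouring endpoint that also counts AIDS is timed from seroconversion

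*Protocol*

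**What the plan says.** Section 10.2.2 gives two time-to-event endpoints for untreated or mixed follow-up, with different starting points:

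- AIDS or death: "Time from enrollment to time of first AIDS-defining event or death".
- Immunologic failure: "Time from seroconversion to immunologic failure will be compared between active microbicide and placebo/control groups". Failure here means two consecutive low CD4+ counts or an AIDS-defining illness.

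The distance between the two starting points is not controlled. Section 5 states that "there is no time limit for MTN-015 enrollment after identification of seroconversion", and section 7.2 says "Participants may enroll anytime after seroconversion". For women who seroconverted before activation, section 5.1 says "study staff will retrospectively contact the participants for possible enrollment in MTN-015". Section 10.3 puts a number on those already more than a year past seroconversion: "We estimate this number to be around 20 such that we will have 172 eligible seroconverters". Section 10.5 keeps such women in the study, since "those participants could be used in the assessment of some of the secondary objectives".

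On method, section 10.6.2 says "Time-to-event secondary endpoints will be analyzed according to the Kaplan-Meier method" and adds a stratified log-rank test. It names no strata and does not mention when a woman enters the risk set.

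**The concern.** For an endpoint meant to show how HIV disease advances, time zero should be a point in the disease. Under the stated definition, a woman enrolled two years after seroconversion starts at time zero beside one enrolled after a month. If the risk of AIDS or death rises with duration of infection, the resulting curve depends on how late the women happened to enroll.

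Two things are at stake. The first is interpretation: the curve cannot be read as progression since infection, and the same AIDS-defining event runs on two different clocks within one section. The second is the comparison of active product with control. Section 10.6.2 concedes that randomization does not make seroconverters comparable across arms. If enrollment lag also differs by arm, or by parent trials with different arm ratios, part of any difference in time to AIDS or death reflects recruitment.

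**Working it through.** **Inputs from the protocol.** 192 seroconverters, 128 control and 64 active; about 20 more than one year past seroconversion; 15% non-enrollment (all section 10.3). The late share is 20/192 = 10.4%. The protocol states no event count, hazard ratio or power for the survival endpoints, so there is no figure of its own to reproduce here.

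**Step 1. Effect on the curve.** Assumptions not in the documents: Weibull time from seroconversion to AIDS or death, shape 1.8, median 7 years; 88% enroll uniformly 0 to 0.5 years after seroconversion and 12% uniformly 1 to 2.5 years after; all are event-free at enrollment.

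- Survival: S(t) = exp(−ln 2 × (t/7)^1.8). Risk by 3 years since seroconversion: 1 − S(3) = 14.0%.
- Risk by 3 years since enrollment at lag L: 1 − S(L+3)/S(L). Averaged over the lags of women still event-free, this is 15.8% for early and 24.9% for late enrollers.
- The probabilities of being event-free at enrollment are 0.998 (early) and 0.942 (late). Overall: (0.88×0.998×15.8 + 0.12×0.942×24.9)/(0.88×0.998 + 0.12×0.942) = 16.9%.

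The enrollment clock thus reads 16.9% where risk since seroconversion is 14.0%. With shape 1.0 (constant hazard) the two agree.

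**Step 2. Which unequal splits fit the protocol.** Late women implied among 128 control and 64 active:

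| Late share, lower vs higher arm | Higher share in active | Higher share in control |
|---|---|---|
| 5% vs 15% | 6.4 + 9.6 = 16 | 19.2 + 3.2 = 22.4 |
| 10% vs 30% | 12.8 + 19.2 = 32 | 38.4 + 6.4 = 44.8 |

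Of these two, only the first row fits around 20.

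**Step 3. Spurious difference at 5% vs 15%, no true effect.** By the Step 1 formula, 3-year risk from enrollment is 16.25% (5% late) and 17.11% (15% late). The ratio of cumulative hazards is ln(1 − 0.1625)/ln(1 − 0.1711) = 0.94; the ratio of risks is 16.25/17.11 = 0.95. Across assumed shapes 1.0 to 2.2, the risk ratio runs from 1.00 to 0.92.

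**Step 4. Behaviour of the log-rank test.** A simulation used 192 × 0.85 = 163 enrollees (109 control, 54 active), 1,500 runs, and no true effect. Assumed: Weibull shape 2, 70% event-free at 5 years, late lag 1 to 2.5 years, other lags up to 3 months, 3.5 to 5.5 years of follow-up. The Monte Carlo standard error near 5% is √(0.05×0.95/1500) = 0.6 points.

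| Late share, control/active | Enrollment origin: rejection, mean HR | Seroconversion with entry at enrollment: rejection, mean HR |
|---|---|---|
| 10% / 10% | 4.5%, 1.01 | 5.3%, 1.01 |
| 40% / 40% | 4.7%, 1.01 | 4.8%, 1.00 |
| 10% / 40% | 9.9%, 1.21 | 4.9%, 1.01 |
| 40% / 10% | 6.9%, 0.86 | 5.3%, 1.03 |

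Equal lag leaves the test at about its nominal level. Unequal lag biases the enrollment-origin comparison in either direction, and the proposed analysis largely removes the bias. The last two rows show direction only: 10% / 40% alone implies 12.8 + 25.6 = 38 late women, far more than the protocol expects.

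**The case against.** Risk from enrollment is a legitimate quantity. It counts only observed follow-up, and calling it inflated against a curve from seroconversion compares two different targets. The endpoint also sits most naturally under the objective to describe clinical events and deaths, which is separate from the objective to compare progression. Late women are only said to be usable for some secondary objectives. Product arms are blinded under section 10.4, and HPTN 059 is expected to supply 0 to 2 seroconverters, so a lag difference by current parent trial has almost no room to arise.

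Much of this stands, and it limits the size of the problem. It does not justify the definition. Section 10.6.2 applies a between-group test to time-to-event secondary endpoints generally, no rule removes late women from this one, the condom-only arm is unblinded, and future trials are to be pooled.

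Three stronger readings are tempting but unsupported:

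- **That the protocol rules out delayed entry.** It is silent. Kaplan-Meier and log-rank methods both accommodate late entry, and an analysis plan not shown may specify it.
- **That immortal time distorts the immunologic-failure endpoint because women who died could not enroll.** Death is not a component of that endpoint, and sections 5.2 and 5.3 do not expressly bar a woman with earlier low CD4+ counts or AIDS-defining illness.
- **That both survival comparisons are necessarily distorted.** Step 4 shows otherwise when lag is equal by arm.

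**Conclusion.** The point holds for the AIDS-or-death endpoint. The protocol fixes an administrative time zero that may fall at any duration of infection, and this conflicts with the clock used for an adjacent endpoint sharing the AIDS component. If hazard rises with duration of infection, the curve does not show progression since infection even when lag is equal across arms.

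Bias between arms is conditional on lag differing by arm or parent trial, which the documents neither show nor exclude. At a late share compatible with about 20 of 192, the effect is likely small: a rate ratio of about 0.94 under no true effect for a 5% versus 15% split. The Weibull shape, the median, the lag ranges, the split and the event-free condition at enrollment are all assumptions. This is a modest correction to a secondary endpoint and does not touch the primary analysis.

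**What to change.** In section 10.2.2, define the endpoint as time from the parent-trial seroconversion date (already defined in section 4.1) to first AIDS-defining event or death. State that each woman enters the risk set at MTN-015 enrollment, or earlier where parent-trial follow-up captured these events, and how a woman with an AIDS-defining event before entry is handled. In section 10.6.2, name parent trial as a stratum of the log-rank test already planned. If risk from enrollment is wanted for description, label it as such. A sensitivity analysis limited to women enrolled within 12 months of seroconversion would show how much late enrollment matters.

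The cost is a few sentences and a little more analysis work. No new data are needed, since visits before ART are already scheduled from the seroconversion date. Risk sets shortly after seroconversion will be slightly smaller, so the early part of the curve will be less precise.
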